2.2 Risk and Benefit

Glaucoma is the second leading cause of visual impairment and blindness worldwide. It results in a substantial economic burden for patients, their families, and society due to sizeable costs of disease management, vision loss, and lost productivity. Current treatment modalities for ACG have significant limitations regarding IOP-lowering effectiveness, adjunctive medication use, requirement for concomitant cataract surgery, complications, and cost. XEN provides effective, minimally invasive, long-lasting, safe, and durable IOP-lowering method through subconjunctival drainage. Use of XEN in patients with ACG might be associated with complications related to narrow angle including aqueous misdirection, cataract formation/progression, choroidal effusion, choroidal hemorrhage, chronic iritis, corneal edema, endothelial touch, flat anterior chamber, hyphema (> 1 week), Gel Implant blockage, iris atrophy, shallow anterior chamber, and suprachoroidal hemorrhage. These risks can be mitigated with appropriate concomitant surgical procedures that widen the angle (eg, cataract extraction, goniosynechiaelysis, iridoplasty). Furthermore, retrospective/case series data available to date on narrow and closed angle patients suggest similar safety as in patients with OAG. Taken together, the benefits outweigh the risks of XEN use in ACG patients.

2.3 Clinical Rationale

Considering the ineffectiveness and complications of the available surgical treatments for controlling IOP in ACG, XEN might offer a safe and effective mode of IOP-lowering.

3. Study Objectives and Clinical Hypotheses

3.1 Study Objectives

The purpose of the trial is to evaluate the safety and IOP-lowering effectiveness of XEN in up to 65 patients with ACG.

3.2 Clinical Hypotheses

XEN will have an IOP-lowering effect and an acceptable safety profile in patients with ACG following implantation.

4. Study Design

4.1 Structure

This is a prospective, multicenter, single-arm, open-label clinical trial designed to demonstrate the safety and IOP-lowering effectiveness of XEN. Following completion of all required preoperative examinations, and if the patient meets the study criteria, XEN will be unilaterally implanted. Approximately 65 patients will be enrolled at up to approximately 15 clinical sites to be unilaterally implanted with XEN and followed for up to 12 months postoperatively.

4.2 Duration

The study will span a total of approximately 14 months including a maximum of 2 months between screening and baseline visits and for up to 12 months for follow-up.

4.3 Treatment Groups and Treatment Regimen

4.3.1 Study Treatment

XEN45 Glaucoma Treatment System, comprised of the XEN Gel Implant and XEN Injector.

4.3.2 Methods for Masking

Not applicable.

4.4 Permissible and Prohibited Medications/Treatments

4.4.1 Permissible Medications/Treatments

Use of concomitant medications other than the prohibited medications (Section 4.4.2) is allowed. The use of any concomitant medication or procedure, prescription or over-the-counter, is to be recorded on the patient's electronic case report form (eCRF) at each visit along with the reason the medication is taken. Prior medications will be recorded as part of the medical history on the participant's eCRF during the first study visit.

Therapy considered necessary for the patient's welfare may be given at the discretion of the investigator. If concurrent medications may have an effect on study outcomes, these medications must be administered in dosages that remain constant throughout the entire duration of the study. If the permissibility of a specific medication/treatment is in question, please contact the sponsor.

Treatment of the fellow (non-study) eye is not restricted, and fellow eyes will receive appropriate medical and/or surgical treatment, including IOP-lowering medications, per the investigator's discretion.

Use of ocular decongestants or antihistamines is allowed if not taken within 2 days prior to a scheduled visit. Ocular decongestants or antihistamines may be restarted 3 days after implantation per the investigator's discretion.

Systemic beta-blocker containing medications are permitted, provided that the dose/dosing regimen has remained stable for at least 2 months prior to screening and is not anticipated to change throughout the duration of the study.

The use of systemic nonsteroidal antiinflammatory drugs is also permitted.

Procedures to widen the iridocorneal angle in the target quadrant (eg, goniosynechialysis, lens extraction [clear lens extraction or cataract surgery/phacoemulsification], and intraocular lens [IOL] placement) are permitted on the operative day (Day 1) at the investigator's discretion; however, all procedures must be successful and uncomplicated for patients to receive XEN. If there are complications that would be significant enough to impact the study results, the patient will be exited from the study. Such complications include, but are not limited to, severe corneal burn, vitreous removal/vitreotomy required, severe anterior chamber injuries, or complications requiring the placement of an anterior chamber lens.

Medications and procedures required for pre-operative, operative, and postoperative management (See Protocol Procedure Manual), including the unlikely event that XEN requires removal for significant safety reasons, are permitted at the investigator's discretion.

4.4.1.1 IOP-lowering Medications

Systemic and topical (study eye only) IOP-lowering medications, will be suspended on the day of surgery (operative day [Day 1]); no washout period is required. They may be introduced postoperatively to manage elevated IOP. At least one of the following criteria must be met to introduce IOP-lowering medications postoperatively:

- Investigator determines IOP is not at target for the patient
- Progression of optic nerve cupping (vertical cup-to-disc ratio)
- Progression of visual field loss (confirmed with a second visual field test within one week).

It is recommended that the medications are prescribed in a step-wise fashion by introducing one drug class at a time. Prior to changing the first postoperative medication or adding subsequent medication(s), the medication must be maintained at a dosage and frequency recommended by the manufacturer's labeling for a reasonable trial period (eg, 1 week). Investigators will consider any contraindications the patient may have previously experienced (eg, allergic reaction or lack of efficacy) and/or the patient's current clinical situation. All changes to the IOP-lowering medication regimen, topical and systemic, will be recorded on the appropriate eCRF.

The investigator may consider discontinuing or lowering the dose or frequency of IOP-lowering medications whenever it is in the interest of patient safety, eg, cases of hypotony (IOP falls below 6 mm Hg).

4.4.2 Prohibited Medications/Treatments

The decision to administer a prohibited medication/treatment is done with the safety of the study patient as the primary consideration. Therapy considered necessary for the patient's welfare may be given at the discretion of the investigator. When possible, the sponsor is to be notified before the prohibited medication/treatment is administered.

Topical and systemic IOP-lowering medications must be suspended on the day of surgery (operative day [Day 1]); no washout period is required. If required, IOP-lowering medications may be introduced postoperatively to manage any elevated IOP (Section 4.4.1.1).

Use of contact lens in the study eye is prohibited during the study.

The following medications (or classes of medications) and treatment procedures are not permitted as concurrent therapy:

- Surgical procedures not related to XEN administration and postoperative management, including other incisional glaucoma treatments, such as trabeculectomy or glaucoma shunt implantation in the study eye, during the study period

- Laser glaucoma treatments, such as laser peripheral iridotomy and laser trabeculoplasty, in the study eye during the study period
- Subconjunctival, sub-Tenon's, intravitreal, or other ophthalmic injections of any medications in the study eye during the study period, with the exception of any medications required for bleb management (Section 6.1.3.2.2)
- Use of any nonstudy topical ophthalmic medications in the study eye, including use of IOP-lowering medications without meeting the criteria specified in Section 4.4.1.1, during the study period, with the exception of ocular decongestants or antihistamines (Section 4.4.1)
- Use of any ophthalmic (including topical, intravitreal, sub-Tenon's, subconjunctival) corticosteroids in either eye from 2 months prior to the baseline visit through study exit, except for use of preoperative, operative, and postoperative topical ocular corticosteroids related to surgery
- Initiation of or alterations in oral, intramuscular, or intravenous corticosteroids from 2 months prior to the baseline visit through the study exit
- Use of LATISSE® (bimatoprost for hypotrichosis) during the study period in the study eye

5. Study Population

5.1 Number of Patients

Approximately 65 patients unilaterally implanted with XEN either as a stand-alone procedure or in combination with lens extraction. A subset of this population will include a maximum of 10 phakic patients (ie, will not undergo lens extraction at time of XEN surgery) and 10 patients with a history of trabeculectomy or glaucoma shunt implantation, to allow for a representative ACG patient population in the study. Sixty-five patients will be implanted to ensure at least 50 evaluable patients with 12 months of follow-up. Patients will be enrolled at approximately 15 clinical sites in the Asia-Pacific and European regions.

5.2 Study Population Characteristics

Adult patients with ACG with uncontrolled IOP after having failed previous medical and/or surgical treatments will be included. If both eyes qualify for inclusion, then the eye with the

higher IOP at baseline will be the study eye. If both eyes qualify for inclusion and have the same baseline IOP, then the right eye will be the study eye. Qualified patients will be unilaterally implanted with the XEN either as a stand-alone procedure or in combination with lens extraction. A subset of this population will include a maximum of 10 phakic patients (ie, will not undergo lens extraction at time of XEN surgery) and 10 patients with a history of trabeculectomy or glaucoma shunt implantation, to allow for a representative ACG patient population in the study.

5.3 Inclusion Criteria

The following are requirements for enrollment into the study:

Non-ocular Criteria for Inclusion

1. Male or female, ≥ 18 years of age and of legal age of consent
2. Signed written informed consent has been obtained
3. Ability to understand and willingness to follow study instructions and is likely to complete all required visits and procedures

Ocular Criteria for Inclusion

4. Diagnosis of ACG defined as areas of ITC present in ≥ 2 quadrants and glaucomatous damage to optic disc and visual field, in the study eye.

Note: Procedures to widen the iridocorneal angle in the target quadrant (eg, goniosynechialysis, lens extraction [clear lens extraction or cataract surgery/phacoemulsification], and IOL placement) are permitted on the operative day (Day 1) at the investigator's discretion; however, all procedures must be successful and uncomplicated for patients to receive XEN. A maximum of approximately 10 phakic patients (ie, will not undergo lens extraction at time of XEN surgery) is allowed in the study.

5. In the opinion of the investigator, the IOP is uncontrolled in the study eye after having failed previous medical and/or surgical treatment (eg, topical IOP-lowering medications, laser peripheral iridotomy, lens extraction, glaucoma shunt implantation, trabeculectomy)

6. IOP of ≥ 20 mm Hg and ≤ 35 mm Hg by Goldmann applanation tonometry in the study eye at screening and baseline (Hour 0)
7. Study eye has healthy, free, and mobile conjunctiva in the target quadrant
8. Glaucomatous visual field loss with a mean deviation score of at least -1 dB in the study eye that, in the opinion of the investigator, is not functionally significant (eg, split fixation, field defect within the central 10 degrees that is visually significant or likely to cause central visual impairment upon progression are excluded)

5.4 Exclusion Criteria

The following are criteria for exclusion from participating in the study:

Non-ocular Criteria for Exclusion

1. Uncontrolled systemic disease (eg, diabetes, hypertension)
2. Female patients who are pregnant, nursing, or planning a pregnancy during the study, or who are of childbearing potential and not using a reliable means of contraception during the study. For purposes of this study, females will be considered of childbearing potential unless they are naturally postmenopausal or permanently sterilized (ie, tubal occlusion, hysterectomy, bilateral salpingectomy, and/or bilateral oophorectomy). Natural menopause is defined as the permanent cessation of menstrual periods, determined retrospectively after a woman has experienced 12 months of amenorrhea without any other obvious pathological or physiological cause
3. Known or suspected allergy or sensitivity to any medications/diagnostic agents (eg, topical anesthetic, dilating drops, fluorescein) required for this protocol or any of the XEN components (eg, porcine products or glutaraldehyde)
4. Known history of bleeding disorder or prolonged bleeding after surgery (in the opinion of the investigator) or those on pharmacologic blood thinners other than aspirin (up to 100 mg/day)
5. Chemotherapy for cancer treatment within 6 months of screening

6. History of dermatologic keloid formation
7. Participation in another drug/device/observational clinical trial concurrently or concluding within 30 days of screening
8. Any condition that would preclude the patient's ability to comply with study requirements, including completion of the study
9. Any condition or a situation which, in the investigator's opinion, may put the patient at significant risk, may confound the study results, or may interfere significantly with the patient's participation in the study

Ocular Criteria for Exclusion

10. Open angle glaucoma, active acute angle closure attack, congenital glaucoma, juvenile glaucoma, secondary glaucomas (eg, anterior subluxation of the lens, iris or ciliary body cysts, active iris and angle neovascularization, iridocorneal endothelial syndrome, anterior uveitis, drug-induced) in the study eye
11. History of following surgeries in the study eye:
 - a. incisional refractive surgery (eg, radial keratotomy), other than astigmatic keratotomy or limbal relaxing incisions
 - b. corneal graft including partial grafts such as Descemet's stripping endothelial keratoplasty and Descemet's membrane endothelial keratoplasty
 - c. previous laser or incisional intraocular surgery that might interfere with the outcome of this trial

However, previous incisional and laser glaucoma surgeries (eg, trabeculectomy, glaucoma shunt implantation, laser trabeculoplasty, iridotomy, cilioablativ e procedures) or uncomplicated phacoemulsification with IOL, occurring more than 3 months prior to screening, are allowed in the study eye. A maximum of 10 patients with a history of trabeculectomy or glaucoma shunt implantation (away from the target quadrant), is allowed in this study.

12. Previous glaucoma shunt implantation in the target quadrant in the study eye

13. Anticipated need for ocular incisional and/or laser surgery in the study eye during the 12-month follow-up period
14. Anticipated use of other topical ocular medications in the study eye except as described in Permissible Medications/Treatments (Section 4.4.1)
15. Ocular (in the study eye) or systemic corticosteroid use within 30 days prior to screening (continuing chronic systemic corticosteroid use is allowed) or known corticosteroid responder
16. Clinically significant inflammation or infection in either eye within 30 days prior to screening (eg, blepharitis, conjunctivitis, keratitis, herpes simplex infection)
17. Active or history of chronic uveitis in the study eye
18. Corneal or other ocular abnormalities (eg, bullous keratopathy, keratoconus) in the study eye that would preclude accurate readings with an applanation tonometer and/or a contact pachymeter, or could confound study results
19. Nanophthalmos in either eye
20. Central corneal thickness ≤ 460 microns or ≥ 620 microns in the study eye
21. Unable to discontinue contact lens wear in the study eye during the study
22. Impaired episcleral venous drainage (eg, Sturge-Weber or other evidence of elevated venous pressure) in the study eye
23. Aphakia, anterior chamber intraocular lens, or previous complicated phacoemulsification surgery in the study eye
24. Vitreous present in the anterior chamber in the study eye
25. Presence of intraocular silicone oil in the study eye
26. Active diabetic retinopathy, choroidal neovascularization, branch retinal vein occlusion, central retinal vein occlusion, proliferative retinopathy, or other ophthalmic disease or disorder in the study eye that could confound study results

27. Visually significant cataract (ie, BCVA 20/40 Snellen equivalent using LogMar chart at screening and baseline) in the study eye that will not be removed at the time of XEN implantation
28. Study eye with best-corrected visual acuity (BCVA) worse than 20/100 (Snellen equivalent using LogMar chart) at screening and baseline; fellow (non-study) eye with BCVA worse than 20/200 at screening and baseline. A patient with a cataract in the study eye and BCVA worse than 20/100 in the study eye may be included if, in the opinion of the investigator, the patient is likely to have BCVA of 20/40 or better after cataract surgery that will be performed at the time of XEN implantation.

6. Procedures

6.1 Procedures to be Performed

Examination visits and visit windows are provided in [Table 1-1](#). The examination requirements for each visit are provided in the following protocol sections and in [Table 1-1](#). It is recommended that the examinations be completed in the order listed, unless otherwise specified.

Visits performed between reporting periods will be documented on an unscheduled visit eCRF. The investigator will report all findings obtained to the sponsor, including IOP measurements, biomicroscopic slit lamp and ophthalmoscopy examination findings, concomitant medications, and AEs.

6.1.1 Screening Visit

The window for this visit is up to 60 days prior to surgery. After obtaining informed consent ([Section 10.1.2](#)), the following information will be obtained at this visit:

- Evaluation of inclusion/exclusion criteria
- Patient demographics
- Medical history, surgical history, ophthalmic history, and ophthalmic surgical history, including presence of ocular pathology and concomitant ocular medications (both eyes)
- Patient ocular symptom questionnaire

- Concomitant medications (systemic and ophthalmic) and procedures
- AEs
- Urine pregnancy test (for females of childbearing potential)
- Manifest refraction (both eyes)
- BCVA using LogMar chart (both eyes)
- Visual field testing (both eyes): Monocular visual field testing will be measured using the Humphrey 24-2 full threshold program or Swedish Interactive Thresholding Algorithm (SITA) Standard and a reliable, interpretable visual field will be obtained for patients with a preoperative BCVA of better than 20/100. This assessment is not required for patients with BCVA of 20/100 or worse. Visual field results must be reliable and interpretable, or if unreliable or uninterpretable, the visual field test must be repeated. An unreliable visual field is defined as visual field measurements with > 33% fixation losses, false positives, or false negatives. Visual field test performed up to 6 months prior to operative day (Day 1) is allowed.
- Biomicroscopic slit lamp examination (both eyes): includes determination of ophthalmic medical observations/complications, evaluation of the condition of the eyelids, conjunctiva, cornea, anterior chamber, iris/pupil, and lens (through a dilated pupil).
- IOP (Hour 0 = 8:00 am \pm 1 hour) measurement using Goldmann applanation tonometry (both eyes) using the 2-person reading method (See Protocol Procedure Manual); IOP must be completed prior to pachymetry, gonioscopy, and ophthalmoscopy.
- Pachymetry measurement of central corneal thickness (both eyes) using an ultrasonic pachymeter
- Gonioscopy (both eyes): includes assessment of angle abnormalities, such as peripheral anterior synechiae, angle assessment of each quadrant by Shaffer Grade

- Ophthalmoscopy (both eyes): includes dilated fundus evaluation and vertical cup-to-disc ratio. Non-dilated ophthalmoscopy may be performed if the investigator believes that pupil dilation may put the patient at risk.

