6.1.2 Baseline Visit

Baseline visit must be performed 5 to 7 days before the surgery. The following tests must be performed on the baseline visit prior to the initiation of preoperative corticosteroid treatment:

- Evaluation of inclusion/exclusion criteria
- Medical history, surgical history, ophthalmic history, and ophthalmic surgical history, including presence of ocular pathology and concomitant ocular medications (both eyes)
- Concomitant medications (systemic and ophthalmic [both eyes]) and procedures
- AEs
- Urine pregnancy test (for females of childbearing potential)
- Manifest refraction (both eyes)
- BCVA using LogMar chart (both eyes)
- Biomicroscopic slit lamp examination (both eyes)
- Diurnal IOP measurement (both eyes): Three IOP measurements taken over an 8-hour period on the same day approximately 4 hours apart, at Hour 0 (± 1 hour), Hour 4 = Hour 0 + 4 hours (± 30 minutes), and Hour 8 = Hour 0 + 8 hours (± 30 minutes). As scheduling permits, the patient must have approximately the same Hour 0 time of day throughout the study. IOP must be completed prior to ophthalmoscopy.
- Ophthalmoscopy (both eyes)

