6.1.4 Follow-up Examinations and Clinical Parameters

The postoperative follow-up duration will be 12 months.

Patients will undergo postoperative visits according to the visit schedule in [Table 1-1](#).

The following information will be obtained for the study eye at the postoperative visits, although not all are required at each visit:

- Patient ocular symptom questionnaire
- Concomitant medications (ophthalmic and systemic) and procedures
- Changes in health that may influence the study outcomes

- AEs
- Manifest refraction, obtained for BCVA testing: to be completed at scheduled visits. In addition, manifest refraction will be performed during any visit if best-corrected visual acuity (BCVA) reduction of ≥ 2 lines is observed since the last BCVA examination.
- BCVA using LogMar chart
- Biomicroscopic slit lamp examination, including assessment for Gel Implant placement and bleb characteristics
- IOP measurement (Hour 0 ± 1 hour) using Goldmann applanation tonometry; IOP must be completed prior to pachymetry, gonioscopy, and ophthalmoscopy.
- Pachymetry measurements of central corneal thickness using an ultrasonic pachymeter
- Gonioscopy
- Ophthalmoscopy

6.1.5 12-Month Postoperative Visit/Early Exit Visit

Patients will be exited from the study once they have completed the 12-month visit.

The following information will be obtained for the study eye:

- Patient ocular symptom questionnaire
- Concomitant medications (ophthalmic and systemic) and procedures
- AEs
- Urine pregnancy test (for females of childbearing potential)
- Manifest refraction
- BCVA using LogMar chart

- Visual field testing: If the visual field assessment at this visit shows progression of visual field loss from baseline (defined as a worsening of at least 3 dB in mean deviation score), a second visual field test must be performed within one week to confirm the progression. If the second visual field test is not confirmatory or is equivocal, a third test must be performed within a week to confirm results.
- Biomicroscopic slit lamp examination, including assessment for Gel Implant placement and bleb characteristics
- Diurnal IOP using Goldmann Applanation Tonometry; IOP must be completed prior to pachymetry, gonioscopy, and ophthalmoscopy.
- Pachymetry measurements of central corneal thickness using an ultrasonic pachymeter
- Gonioscopy
- Ophthalmoscopy

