**Visual Field Test:** Visual field tests will be performed at baseline and at Month 12/Early Exit visits. Number and percent of patients with an abnormal visual field in SE will be presented by visit and abnormality condition (Enlargement of blind plot, Superior arcuate scotoma, Inferior arcuate scotoma, Paracentral scotoma, Nasal step, Central scotoma, Generalized depression, Temporal scotoma, or Other). Note that a patient may have more than one abnormality condition. Further, visual field mean deviation and change from baseline to Month 12/Early Term will also be descriptively summarized. A change (Month 12/Early Term – Baseline) in visual field mean deviation measured using the same program of > 3.0 dB will be categorized as ‘Better’, a change of -3.0 dB to +3.0 dB will be categorized as ‘no change’ and a change of <-3.0 dB will be categorized as ‘Worse’. Number and percent of patients belonging to each the three categories will also be presented.

**Pachymetry:** Contact pachymetry will be performed at screening and Month 12/Early exist. Three measurements of central corneal thickness and their average are recorded. These average values will be summarized by visit. Changes from screening to Month 12/Early exit visit will also be summarized.

**Gonioscopy:** Gonioscopy exams will be performed at screening, month 1, 6 and 12/Early Exit. The findings will be summarized by visit.

**Ocular Biomicroscopic Exam:** These exams will be performed at screening, baseline, Day 2, Day 8, Week 2, Months 1, 3, 6, 8, 10 and 12/Early Exit. At each of these exams, any findings related to Eyelids/Eyelid Margins/Lashes, Conjunctiva (Bulbar of

Palpebral), Cornea, Anterior Chamber, or Iris/Pupil are noted (yes, no, not evaluable) will be recorded. Number and percent of patients showing findings in each of the above areas will be summarized by visit. Further, associated with each eye, symptom severity data except for 'Iris/Pupil' will also be collected for the sub-categories described below:

- Eyelids/Eyelid Margins/Lashes:
  - Erythema
  - Edema
  - Other
- Conjunctiva:
  - Hyperemia
  - Edema
  - Subconjunctival Hemorrhage
  - Pterygium, encroaching on visual axis
  - Pterygium, not encroaching on visual axis
  - Other
- Cornea (Central, Peripheral, or Central and Peripheral):
  - Filaments
  - Infiltrates
  - Edema
  - Corneal Guttata
  - Endothelial Pigment
  - Keratic Precipitates
  - Neovascularization
  - Opacity
  - Stromal Haze
  - Other
- Anterior Chamber:

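### The baseline visual field can predate a permitted eye operation, and a nominal 12-month field change can span up to about 18 months

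*Protocol*

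**What the plan says.** Table 1-1 schedules visual field testing at Screening and at Month 12/early exit only; the baseline visit has none. Protocol 6.1.1, footnote e of Table 1-1 and footnote e of SAP Table 4-1 all carry the same allowance: "Visual field test performed up to 6 months prior to operative day (Day 1) is allowed". The Screening visit is timed as follows: "The window for this visit is up to 60 days prior to surgery". For the visit after it: "Baseline visit must be performed 5 to 7 days before the surgery".

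Exclusion criterion 11c (Protocol 5.4) rules out "previous laser or incisional intraocular surgery that might interfere with the outcome of this trial". The sentence after it makes an exception: incisional and laser glaucoma procedures and uncomplicated phacoemulsification, "occurring more than 3 months prior to screening, are allowed in the study eye". Patients with earlier trabeculectomy or shunt implantation are capped at 10; earlier phacoemulsification and laser are not capped.

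SAP 16.1 defines baseline as any day up to Day 1, with no lower limit, and takes the assessment closest to the target day when a window holds several. SAP 11.3 states that "visual field mean deviation and change from baseline to Month 12/Early Term will also be descriptively summarized". It then sorts eyes into Better, no change and Worse, where "a change of <-3.0 dB will be categorized as" Worse.

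**The concern.** The two look-back rules are measured from different dates and are not tied to each other. The field's age is counted back from Day 1, while the surgery limit is counted back from screening. An eye can therefore enter with a field taken before its last operation, and that field can become the baseline for change after XEN.

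Two distortions are possible. If the field was taken before an operation that improved it, such as removal of a cloudy lens, the gain can offset loss after XEN. If the field was already declining before the implant, that loss is counted as change after XEN. Visual field is a named ocular safety measure (Protocol 7.2) with one scheduled follow-up test, and the trial is single-arm (Protocol 4.1). No control group would share these effects and let them cancel.

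**Working it through.** The plan gives no figure of its own on this point, so the check is calendar arithmetic.

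**Inputs from the documents**
- Oldest accepted field: 6 months, about 183 days, before Day 1 (Protocol 6.1.1).
- Latest permitted earlier operation: just over 3 months, about 91 days, before screening (Protocol 5.4).
- Screening lead *s*: at most 60 days before Day 1 (Protocol 6.1.1). I take screening to be no later than the baseline visit, so *s* is at least 5 to 7 days (Protocol 6.1.2).
- Follow-up: Month 12 target is Day 366, which is 365 days after implant (SAP 16.1).

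**Step 1. Can the field predate a permitted operation?** The latest operation falls *s* + 91 days before Day 1. The longest time by which the field can precede it is 183 − (*s* + 91).

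| Screening lead *s* (days) | Latest permitted operation (days before Day 1) | Field can precede it by up to (days) |
|---|---|---|
| 5 | 96 | 87 |
| 7 | 98 | 85 |
| 30 | 121 | 62 |
| 60 | 151 | 32 |

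With unrounded months of 30.44 days the last column is 91.3 − *s*, or 86, 84, 61 and 31 days. The range is about 31 to 87 days, and the overlap exists at every permitted screening date.

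**Step 2. How much of the measured change is before the implant?** Share = pre-implant days / (pre-implant days + follow-up days).
- Oldest field, Month 12: 183 / (183 + 365) = 183/548 = 33%.
- Oldest field, early exit at about 6, 3 or 1 month (182, 91, 30 days): 50%, 67%, 86%.
- Field at the 60-day limit, Month 12: 60 / (60 + 365) = 14%.

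**Step 3. Would a field from the 60-day period solve the ordering?** Yes. The latest permitted operation is at least 96 days before Day 1, so a field from the last 60 days must follow it.

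**Step 4. Can the effect be sized in dB?** Not from the documents, which give neither a rate of decline, nor a gain from surgery, nor an SD for the change. Assumed declines of 0.5, 1, 2 and 3 dB/year would add 0.25, 0.5, 1.0 and 1.5 dB over 6 months, or 8%, 17%, 33% and 50% of the 3 dB cut. For a single normally distributed reading, P(Worse) = Φ((−3 − mean change)/SD):

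| Assumed mean change | SD 1 dB | SD 2 dB | SD 3 dB |
|---|---|---|---|
| 0 (stable eye) | 0.1% | 6.7% | 15.9% |
| −0.75 (stable after XEN, 0.75 dB lost before) | 1.2% | 13.0% | 22.7% |
| −3.5 (true loss after XEN) | 69% | 60% | 57% |
| −2.5 (same loss, 1 dB earlier gain) | 31% | 40% | 43% |
| −1.5 (same loss, 2 dB earlier gain) | 7% | 23% | 31% |

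These are per-eye illustrations for an affected eye. They show that the result depends on inputs the plan does not supply; they do not estimate an effect on the study.

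**The case against.** The strongest reply is that the older field is an allowance, not the rule. Visual field is a scheduled Screening examination, and the closest-to-target rule in SAP 16.1 lets a Screening field displace an older one whenever both are on file. The ordering problem needs an old field used alone and also an operation between that field and screening. The documents do not say how many eyes meet both conditions. This stands, and it limits the point to what *can* happen in some eyes.

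Second, lens extraction at the XEN operation is permitted, so those eyes have a pre-extraction baseline however recent the field. This also stands: it is a separate source of confounding that a newer field does not remove.

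Third, the consequence is small. SAP 10.0 tests no formal hypothesis, the field summary is descriptive, and Protocol 8.3.4 does not list it among the planned safety summaries. The IOP and medication endpoints and the sample size are untouched. I agree.

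The other safeguards do not close the gap. Criterion 11c is a judgement followed by an express exception. The same-methodology rule in Protocol 7.2 fixes the test program, not its date. Protocol 6.1.5 calls for repeat testing after progression, "defined as a worsening of at least 3 dB in mean deviation score", but this re-examines the follow-up field and leaves the baseline as it was.

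**Conclusion.** The gap is real and minor. At every permitted screening date the rules allow a baseline field that precedes a permitted operation, by up to about 31 to 87 days. They also allow a nominal 12-month change of up to about 548 days, a third of it before the implant. Both hold only for eyes with no newer pre-implant field.

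A reader might infer three stronger things that the documents do not support:
- **That the reported change generally contains pre-implant decline or another operation's effect.** Only some eyes can be affected, and their number is unknown.
- **That eyes with an old field had up to six months of uncontrolled pressure before the implant.** Inclusion criteria 5 and 6 establish uncontrolled IOP at entry, not its duration.
- **That the safety result is biased in a known direction or by a known amount.** The two effects oppose each other, and any size in dB rests on assumed inputs.

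The calendar results assume months of about 30.4 days and screening no later than the baseline visit.

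**What to change.** In Protocol 6.1.1, footnote e of Table 1-1 and footnote e of SAP Table 4-1, add: *A field performed before Screening may be used only if it was obtained after the most recent laser or incisional procedure in that eye; otherwise the field is done at Screening.* Keep the existing exemption in 6.1.1 for BCVA of 20/100 or worse.

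This closes the ordering gap but still lets an eye without recent surgery use a field up to 6 months old. For that, in SAP 11.3 repeat the mean-deviation change and the three-category table for eyes whose baseline field was obtained within the 60-day screening period and after any earlier procedure. This lowers the largest pre-implant share at Month 12 from 33% to 14%. Show it separately for eyes with and without lens extraction at the XEN operation; this displays that confounding but does not remove it.

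The cost is one protocol sentence, a small set of descriptive tables, and a Screening field, already scheduled, in the recently operated eyes that would have relied on an older one. The subset tables will be smaller and less precise. If enrolment is complete, the SAP part can still be done where actual test dates were recorded. SAP 16.1 substitutes the visit date when the assessment date is missing, which would hide a field's age, so eyes without a recorded test date should be identified.
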